4.3 Discontinuation and Withdrawal

4.3.1 Discontinuation of Study Treatment

Subjects must discontinue study treatment if any of the following criteria are met:

- 1. Any AE that meets the treatment discontinuation criteria specified in the protocol (refer to Section 5.3).
- 2. Disease progression. (Subject who meets the criteria for treatment beyond progression may continue treatment until confirmation of progressive disease by tumor assessment. Refer to Section 3.1.2.1.)
- 3. Subjects who receive any prohibited treatment during the trial that compromises the assessment of safety and efficacy may be determined to discontinue study treatment by the investigator in consultation with the sponsor medical monitor.
- 4. Any intercurrent condition that compromises the subject's ability to continue study treatment.
- 5. Pregnancy of female subjects.
- 6. Subjects and/or their legal guardian who decide to discontinue the study treatment may inform the subject's doctor at any time and then discontinue study treatment. According to the Deceleration of Helsinki and other applicable regulatory requirements, all subjects have the right to withdraw from the study at any time and for any reason. The doctor and the study site must not hold bias in their future treatment.
- 7. Subject with poor compliance who doesn't receive treatment at the right dose and the right time despite the investigator's effort in communication and coordination, which may lead to significant uncorrectable bias in the study results may be determined to discontinue study treatment by the investigator in consultation with the sponsor medical monitor.
- 8. Other conditions that make study treatment continuation inappropriate judged by the investigator.

In any case, the primary reason for study treatment discontinuation will be recorded in the original medical record. For subjects who discontinue study treatment for any reason, the investigator should try every effort to have the subject complete end of study visit if the subject has received at least one dose of the investigational product, and continue to follow up subjects with unresolved AE.

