5.3.2 Criteria for Dose Modification of Investigational Product

Dose increase or reduction of CS1001 is not permitted in this trial. The investigational product will be **withheld** for any of the following investigational drug-related adverse reactions:

- 1. Grade 2 pneumonitis
- 2. Grade 2 or 3 colitis; Grade 3 diarrhea or persistent Grade 2 diarrhea
- 3. Grade 2 hepatitis (elevation of ALT, AST, or total bilirubin levels)
- 4. Grade 2 hypophysitis without adrenal crisis
- 5. Grade 2 nephritis
- 6. Grade 3-4 hypothyroidism
- 7. Grade 3 hyperthyroidism lasting for 6 weeks or more despite proper management
- 8. Grade 3 dermatitis
- 9. Grade 2 neuromuscular toxicity
- 10. Grade 2 ocular toxicity
- 11. Other Grade 2 AEs (for example arthritis, pancreatitis, hemolytic anemia, adrenal insufficiency, myasthenic syndrome, and rhabdomyolysis)
- 12. Grade 4 hematologic toxicity
- 13. Any Grade 3 abnormal laboratory test results except for the following situations:
 - Grade 3 hematologic toxicity.

- Study treatment will be delayed when Grade 2 hepatitis occurs.
- 14. Any AE, abnormal laboratory test result, or intercurrent condition that in the investigator's opinion requires postponing study treatment.

Subjects may resume investigational treatment when the above AE(s) resolve(s) to Grade 0/1 or baseline and the dose of systemic corticosteroid for treating the AE(s) have been tapered to 10 mg daily prednisone equivalents or less.

The investigational treatment will not be resumed for dosing delay due to any cause for more than **9 weeks** (12 weeks after the last dose). (Subject may continue treatment if he/she still benefits clinically at the discretion of investigator in consultation with the sponsor's medical monitor.)

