5.3.3 Criteria for Permanent Discontinuation of Investigational Treatment

The investigational product will be **permanently discontinued** after consultation with the sponsor's medical monitor for any of the following drug-related adverse events:

- Grade 3-4 pneumonitis
- Grade 4 colitis, recurrent Grade 3 colitis, or colitis with symptom suggestive of intestinal perforation
- Grade 3 hepatitis (elevation of ALT, AST, or total bilirubin levels)
- Grade 4 abnormal laboratory test results except for the following situations:

-Grade 4 neutropenia lasting for \leq 5 days

-Grade 4 lymphocytopenia or leukopenia

- Solitary Grade 4 electrolyte disorder/imbalance that can be corrected by electrolyte supplementation/adequate treatment in 72 hours without any clinical consequence.

- Grade 3-4 hypophysitis or adrenal crisis
- Grade 3-4 nephritis
- Grade 4 hyperthyroidism
- Grade 4 dermatitis
- Grade 3-4 neuromuscular toxicity
- Grade 3-4 ocular toxicity
- Other Grade 3-4 AEs (for example arthritis, pancreatitis, hemolytic anemia, adrenal insufficiency, myasthenic syndrome, and rhabdomyolysis) except for Grade 3/4 hypothyroidism
- Grade 4 infusion-related reactions

Permanent discontinuation of investigational product will be considered for recurrence of any of the following Grade ≥ 2 irAEs: pneumonitis, ocular toxicity, cardiac toxicity, and at the discretion of the investigator.

For subjects who meet any of the above criteria although benefiting from investigational treatment, the sponsor's medical monitor and the investigator will discuss and make the final decision in the subject's best interest.

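### Section 5.3.2 item 13 has a misworded exception: drug-related Grade 3 ALT, AST and bilirubin elevations fall under hold-and-restart as well as under the permanent stop in 5.3.3 and Appendix 13.4

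*Protocol*

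**What the plan says.** Protocol section 5.3.2 lists the drug-related reactions for which CS1001 is withheld. Two items concern the liver:

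- Item 3 is "Grade 2 hepatitis (elevation of ALT, AST, or total bilirubin levels").
- Item 13 is "Any Grade 3 abnormal laboratory test results except for the following situations". Two situations follow: Grade 3 hematologic toxicity, and the sentence "Study treatment will be delayed when Grade 2 hepatitis occurs".

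The restart rule covers the whole list: "Subjects may resume investigational treatment when the above AE(s) resolve(s) to Grade 0/1 or baseline", provided that any systemic steroid given for the event is down to 10 mg prednisone equivalent a day or less.

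Section 5.3.3 sets permanent discontinuation, "after consultation with the sponsor's medical monitor for any of the following drug-related adverse events". Its list includes "Grade 3 hepatitis (elevation of ALT, AST, or total bilirubin levels"). A closing paragraph, beginning "For subjects who meet any of the above criteria although benefiting from investigational treatment", leaves the final decision for such subjects to the medical monitor and the investigator together.

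The hepatitis row of Appendix 13.4 counts asymptomatic liver-test elevations as hepatitis. It gives permanent discontinuation at Grade 3 or higher, and prints a bilirubin limit of more than 3 times ULN beside that instruction.

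Section 4.3.1 opens with "Subjects must discontinue study treatment if any of the following criteria are met". Its first criterion is an AE that meets the discontinuation criteria in section 5.3.

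**The concern.** An exception to a Grade 3 rule has to name something at Grade 3. The second exception in item 13 names a Grade 2 event and tells the site to delay dosing, which item 3 already does. Nothing in item 13 therefore takes Grade 3 liver results out of the general laboratory rule, and the site has two instructions for the same finding: hold and possibly restart, or stop for good.

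What is at stake is a dosing decision in a subject with liver toxicity. Section 5.3.1 names hepatitis among the immune-related events seen with other checkpoint inhibitors, and Table 1 footnote 12 schedules ALT, AST and bilirubin before each dose from Cycle 2, so sites will consult these rules routinely.

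**Working it through.** There is no figure to reproduce. The check is to put the rules side by side for a drug-related elevation of ALT, AST or total bilirubin.

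| Grade | 5.3.2 item 3 | 5.3.2 item 13 as printed | 5.3.3 | Appendix 13.4, hepatitis row |
|---|---|---|---|---|
| 2 | hold | second exception: delay | not listed | hold until Grade 1 or lower |
| 3 | not listed | hold, restart allowed | permanent stop | permanent stop |
| 4 | not listed | not listed | permanent stop (Grade 4 laboratory item) | permanent stop |

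1. **Grade 2.** All the rules that speak agree. The second exception adds nothing to item 3.

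2. **Grade 3.** Item 13 covers every drug-related Grade 3 laboratory result apart from its exceptions. The hematologic exception does not reach liver tests, and the hepatitis sentence is confined to Grade 2. Grade 3 liver results therefore stay in item 13 and come under the restart rule. Section 5.3.3 and Appendix 13.4 both say stop.

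3. **Grade 4.** There is no conflict. The exceptions to the Grade 4 laboratory item in 5.3.3 are blood counts and correctable electrolyte disorders, not liver tests.

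4. **How the slip probably arose.** The Version 3.0 amendment log adds a general laboratory scheme: hold at Grade 3 in 5.3.2 and stop at Grade 4 in 5.3.3. The hepatitis scheme is one grade stricter: hold at Grade 2, stop at Grade 3. The second exception is where liver tests should leave the general scheme, but its wording does not do that. The log carries the same sentence, so it is not a text-extraction error.

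5. **Does separating a laboratory result from hepatitis remove the overlap?** Not as the rules are written. Section 5.3.3 glosses hepatitis as these same elevations, and Appendix 13.4 includes the asymptomatic ones.

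6. **Which rule prevails?** Section 4.3.1 is mandatory once an AE meets the discontinuation criteria, whereas the restart clause in 5.3.2 is only permissive. For an event recognised as Grade 3 hepatitis, the stop governs.

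7. **Where the wording can still change a decision.** Section 7.3.2 grades an AE tied to a laboratory finding by the clinical severity of the underlying condition, which need not match the laboratory grade. A site could therefore class an asymptomatic Grade 3 ALT as a laboratory finding only, apply item 13, and hold and restart instead of stopping.

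8. **The overlap is not confined to the liver.** Section 5.3.3 stops treatment permanently for Grade 3-4 nephritis, and Appendix 13.4 lists raised serum creatinine among the signs of nephritis. A Grade 3 creatinine result also falls under item 13 as printed.

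**The case against.** The strongest reply is that the protocol already resolves the matter. Section 4.3.1 requires discontinuation, a subject who meets 5.3.3 cannot resume merely because a broader hold item also applies, and 5.3.1 directs sites to Appendix 13.4. The clumsy sentence can also be read as a hint that for the liver the hold begins at Grade 2, so that liver tests follow the hepatitis rules throughout. Practical safeguards exist too. Section 7.4 asks for repeat testing of clinically significant Grade 3 or 4 results and for action in consultation with the medical monitor, and 7.6 sends specified liver findings to the sponsor within 24 hours.

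Much of this stands. The stop does prevail for recognised Grade 3 hepatitis, and the hinted reading is probably what was intended. But the sentence does not say so, and 7.3.2 leaves room for a different classification. Section 7.6 is a reporting rule and not a dosing rule, and each of its triggers needs a transaminase rise, so an isolated bilirubin elevation falls outside it.

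A reader might go further and infer that the protocol has no effective stop rule for Grade 3 liver toxicity, or that it authorises restart after Grade 3 hepatitis. The documents support neither: 5.3.3, Appendix 13.4 and 4.3.1 together supply the stop. A reader might also infer that every Grade 3 laboratory value must trigger the stop by laboratory grade alone. The hepatitis criteria do not state that grading basis, and it would sit against 7.3.2.

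**Conclusion.** Item 13 is wrong as written and worth correcting. Its second exception excludes no Grade 3 result, so drug-related Grade 3 ALT, AST and bilirubin elevations carry both a hold-and-restart instruction and a permanent stop. The consequence is limited to a contradictory site instruction on a safety rule, with the stop prevailing once Grade 3 hepatitis is recognised.

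The number of subjects affected cannot be estimated, because the documents give no rate of Grade 3 liver results. No effect on ORR or on any other analysis is claimed. The conclusion rests on the printed text of 5.3.2, 5.3.3, 4.3.1, 7.3.2 and Appendix 13.4, and on no assumed event rate. That the wording could change a decision in practice assumes a site that classes an asymptomatic Grade 3 result as a laboratory finding under 7.3.2. The documents do not show how often that would happen.

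**What to change.** Replace the second exception in 5.3.2 item 13 with:

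> Grade 3 elevation of ALT, AST or total bilirubin, or any other Grade 3 result that meets a 5.3.3 criterion (for example Grade 3 nephritis): follow 5.3.3 and Appendix 13.4 (Grade 2 hepatitis is withheld under item 3).

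Leave the medical monitor consultation and the provision for benefiting subjects in 5.3.3 unchanged. Do not add a requirement to grade by laboratory value. If the sponsor wants one, it is a substantive change that has to be reconciled with 7.3.2.

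The cost is one line in a clarification letter or the next amendment, with no new data or procedures.

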5.3.3 Criteria for Permanent Discontinuation of Investigational Treatment

The investigational product will be **permanently discontinued** after consultation with the sponsor's medical monitor for any of the following drug-related adverse events:

- Grade 3-4 pneumonitis
- Grade 4 colitis, recurrent Grade 3 colitis, or colitis with symptom suggestive of intestinal perforation
- Grade 3 hepatitis (elevation of ALT, AST, or total bilirubin levels)
- Grade 4 abnormal laboratory test results except for the following situations:

-Grade 4 neutropenia lasting for \leq 5 days

-Grade 4 lymphocytopenia or leukopenia

- Solitary Grade 4 electrolyte disorder/imbalance that can be corrected by electrolyte supplementation/adequate treatment in 72 hours without any clinical consequence.

- Grade 3-4 hypophysitis or adrenal crisis
- Grade 3-4 nephritis
- Grade 4 hyperthyroidism
- Grade 4 dermatitis
- Grade 3-4 neuromuscular toxicity
- Grade 3-4 ocular toxicity
- Other Grade 3-4 AEs (for example arthritis, pancreatitis, hemolytic anemia, adrenal insufficiency, myasthenic syndrome, and rhabdomyolysis) except for Grade 3/4 hypothyroidism
- Grade 4 infusion-related reactions

Permanent discontinuation of investigational product will be considered for recurrence of any of the following Grade ≥ 2 irAEs: pneumonitis, ocular toxicity, cardiac toxicity, and at the discretion of the investigator.

For subjects who meet any of the above criteria although benefiting from investigational treatment, the sponsor's medical monitor and the investigator will discuss and make the final decision in the subject's best interest.

5.3.4 Infusion-Related Reaction

The symptoms of infusion-related reactions include fever, chills, nausea, pruritus, angioedema, hypotension, headache, bronchospasm, urticaria, rash, vomiting, myalgia, dizziness, or hypertension. Severe reactions may include acute respiratory distress syndrome, myocardial infarction, ventricular fibrillation, and cardiogenic shock. Subjects should be closely monitored for such reactions. Treatment modification for symptoms of infusion-related reactions due to CS1001 is presented in Table 2.

Immediate access to an Intensive Care Unit (ICU) or equivalent environment and appropriate medical care (including epinephrine, corticosteroids, IV antihistamines, bronchodilators, and oxygen) must be available to treat infusion-related reactions in the study sites. Infusion of CS1001 will be discontinued in case of Grade ≥ 2 infusion-related, allergic, or anaphylactoid reactions. Subjects must be closely monitored for infusion-related reactions continuously for 2 hours after the first two doses of CS1001.

CTCAE Grade	Treatment Modification for CS1001	
Grade 1 Mild transient reaction; infusion interruption not indicated; intervention not indicated.	CS1001 infusion rate is decreased by 50% and any worsening of the reaction is closely monitored until its resolution.	
Grade 2 Therapy or infusion interruption indicated but responds promptly to symptomatic treatment (e.g., antihistamines, NSAIDs, narcotics, IV fluids); treatment of prophylactic medications ≤24 hours.	decreased to Grade ≤ 1 in severity and any	
Grade 3 Prolonged (e.g., not rapidly responsive to symptomatic treatment and/or brief interruption of infusion); recurrence of symptoms following initial improvement; hospitalization for clinical sequelae or cause clinical consequences (for example kidney injury or pulmonary infiltration).	CS1001 infusion is immediately discontinued. Continuation of study therapy is at the discretion of the investigator.	
Grade 4 Life-threatening consequences; urgent intervention (for example mechanical ventilation) indicated.	Subjects must permanently discontinue CS1001 treatment.	

Table 2 Treatment Modification for Symptoms of Infusion-Related Reactions

NSAIDs, non-steroidal anti-inflammatory drugs.

Once the CS1001 infusion rate has been decreased by 50% or suspended due to an infusion-related reaction, it must remain decreased for all subsequent infusions. If the subject has a second infusion-related reaction (Grade ≥ 2) on the slower infusion rate, the infusion should be stopped, and the subject should be permanently discontinued from CS1001 treatment.

CTCAE Grade 1 or 2 infusion reaction: Proper medical management should be instituted, as indicated per type of the reaction. This includes but is not limited to an antihistamine (e.g., diphenhydramine or equivalent), antipyretic (e.g., paracetamol or equivalent), and oral or IV corticosteroids, epinephrine, bronchodilators, and oxygen on demand. The subject should receive bedside monitoring until symptoms resolve. In the following cycles, subjects should 42/104

receive oral prophylactic treatment with an antihistamine (e.g., diphenhydramine or equivalent) and an antipyretic (e.g., paracetamol or equivalent) at least 30 minutes before the start of the infusion, and they should be closely monitored for clinical signs and symptoms of an infusion-related reaction.

CTCAE Grade 3 or 4 infusion reaction: Immediately stop the infusion. Proper medical management should be instituted immediately, per type and severity of the reaction. This includes but is not limited to oral or IV anti-histamine, anti-pyretic, corticosteroids, epinephrine, bronchodilators, and oxygen.

If a subject experiences a Grade 4 infusion-related reaction at any time, CS1001 must be discontinued permanently.

In the event of a Grade 3 infusion-related reaction, the continuation of study therapy is at the discretion of the investigator after consultation with the sponsor's medical monitor. If continued, the infusion time of CS1001 in the next cycle should be at least 2 hours. Subjects should receive oral prophylactic treatment with an anti-histamine (e.g., 50 mg diphenhydramine or equivalent) and an antipyretic (e.g., paracetamol, NSAIDs or equivalent) 30-60 minutes before the start of the infusion. Subjects should be closely monitored for clinical signs and symptoms of an infusion-related reaction.

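### The Section 5.3.3 exception for benefiting subjects is not closed for Grade 4 infusion-related reactions, although Section 5.3.4 and Table 2 require permanent discontinuation

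*Protocol*

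**What the plan says.** Protocol Section 5.3.3 gives the criteria for permanent discontinuation. Its lead-in has CS1001 stopped once the sponsor's medical monitor has been consulted, for any drug-related event on the list. The last item on that list is "Grade 4 infusion-related reactions". The section closes with an exception, which covers a broad group: "For subjects who meet any of the above criteria although benefiting from investigational treatment". What happens to them is left to a joint discussion and final decision by the monitor and the investigator, guided by what is best for the individual.

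Section 5.3.4 deals with infusion-related reactions specifically.

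- Grade 4, Table 2: "Subjects must permanently discontinue CS1001 treatment".
- Grade 4, text: "If a subject experiences a Grade 4 infusion-related reaction at any time, CS1001 must be discontinued permanently".
- Grade 3, Table 2: "Continuation of study therapy is at the discretion of the investigator".
- Grade 3, text: "In the event of a Grade 3 infusion-related reaction, the continuation of study therapy is at the discretion of the investigator", after the medical monitor has been consulted. If treatment goes on, the infusion time in the next cycle "should be at least 2 hours. Subjects should receive oral prophylactic treatment with an anti-histamine" and an antipyretic beforehand.

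**The concern.** Two instructions in the same part of the protocol cover the same event and do not agree. Section 5.3.4 separates the grades: a joint decision after Grade 3, none after Grade 4. Read literally, the closing sentence of Section 5.3.3 gives a benefiting subject with a Grade 4 reaction the kind of investigator-and-monitor decision that Section 5.3.4 keeps for Grade 3.

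Table 2 describes Grade 4 as life-threatening, with mechanical ventilation as an example of the intervention needed. At stake is whether such a subject could be given CS1001 again under the protocol. A second matter is record-keeping: one site could regard the dose as allowed under Section 5.3.3, while another records it as a deviation from Section 5.3.4.

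**Working it through.** No arithmetic applies. The check sets the relevant texts of protocol Version 3.0 side by side.

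| Place | Rule for a Grade 4 infusion-related reaction | Room to continue? |
|---|---|---|
| 5.3.3, list | Permanent discontinuation, after consultation | Not in the list itself |
| 5.3.3, closing sentence | Final decision by monitor and investigator if the subject is benefiting | Left open; no item excluded |
| 5.3.4, Table 2 | Mandatory permanent discontinuation | None; Grade 3 only |
| 5.3.4, text | Mandatory permanent discontinuation, whenever it occurs | None; Grade 3 only |
| 4.3.1, item 1 | Stop for events meeting the criteria in Section 5.3 | Does not say which part of 5.3 governs |
| Appendix 13.4 | No row for infusion-related reactions | Silent |

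**Is the event inside the exception?** Yes. It is named in the list, and the closing sentence reaches every listed criterion.

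**Does any text rank the two rules?** No. Section 5.3.3 does not refer to Section 5.3.4. Section 4.3.1 opens with a mandatory stop, but its first item points to Section 5.3 as a whole, which contains both rules.

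**Does the closing sentence permit re-dosing?** Not expressly. Where the protocol means to allow continuation it says so: Section 5.3.2 states that a subject who still benefits clinically may continue after an over-long dosing delay. Section 5.3.3 says only who decides and by what standard. On the other hand, the list already requires discontinuation after consultation, so a separate sentence for benefiting subjects has a purpose only if some other outcome is possible for at least some criteria.

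**What would govern a further dose?** After Grade 3, Section 5.3.4 sets premedication and an infusion of at least 2 hours. It has no counterpart for Grade 4, since it foresees no further dose. Its general rule that a reduced infusion rate stays reduced is not specific to Grade 4.

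**Is this the only listed criterion with the pattern?** No. Section 5.3.3 has 12 criteria. Appendix 13.4 states permanent discontinuation, with no benefit exception, in its rows for pneumonitis, colitis, hepatitis, hypophysitis, nephritis, hyperthyroidism, dermatitis, neuromuscular toxicity, ocular toxicity and other immune-related events. That is 10 of the other 11; the remaining one is Grade 4 laboratory abnormalities. Appendix 13.4 is headed as guidance, however. Infusion reactions are the clearest case because body text and a table both use mandatory language and keep discretion for the lower grade.

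**Does the ORR analysis depend on it?** No. The protocol and SAP define the efficacy analysis set by at least one dose and central pathology confirmation, so a deviation does not remove a subject. Response is by independent review of imaging.

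**The case against.** The strongest reply is that the specific rule governs the general one. Section 5.3.4 states the prohibition twice and without condition, and a site managing an infusion reaction would turn to the section with that title. The two texts can also be reconciled: Section 5.3.3 says who decides, and Section 5.3.4 fixes the answer for Grade 4. The exception still has work to do for the other 11 criteria. This is probably what was intended, and it stands as the better reading. It does not remove the problem, because the protocol never states that order and Section 5.3.3 names Grade 4 infusion reactions in the list to which its exception applies.

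A second reply is that safeguards exist. The exception needs both the investigator and the sponsor's medical monitor, and a life-threatening reaction is a serious adverse event reportable within 24 hours (Sections 7.2.1 and 7.2.2). That also stands: no reading lets a site use the exception alone. It lowers the chance of harm but does not settle which rule applies.

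A reader might go further and infer that Section 5.3.3 authorises re-dosing after a Grade 4 reaction. The text does not support that; it leaves the matter open without granting permission.

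A reader might also infer that the exception can matter only late in treatment, because imaging evidence of benefit must wait for the first scheduled scan at Week 12. That does not follow either. Section 5.3.2 allows dosing to be delayed by up to 9 weeks, that is, to 12 weeks after the last dose. A subject who reacts at the first dose could therefore still be under consideration at Week 12. Section 5.3.3 also does not define benefit, so clinical judgement could be used sooner.

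**Conclusion.** The inconsistency is real and lies in the current body text. It is an ambiguity between two stated safety rules and should be corrected. It leaves open re-dosing after a life-threatening infusion reaction, without Grade 4-specific safeguards and with unclear deviation status. The conclusion rests on a literal reading of the closing sentence of Section 5.3.3 and on the absence of any stated precedence.

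Its size cannot be expressed as a probability, since the documents give no incidence of Grade 4 infusion reactions. Nor should it be presented as a conflict confined to one of 12 criteria, given the wording of Appendix 13.4; it is the clearest instance of a wider pattern. The consequences are limited to subject safety and deviation classification. The ORR estimate, its confidence interval and the analysis sets do not depend on it.

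**What to change.** Make two edits to Section 5.3.3.

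1. In the closing sentence, directly after the reference to the criteria above, insert: *except Grade 4 infusion-related reactions, for which CS1001 must be permanently discontinued without exception (Section 5.3.4)*.
2. Add to the lead-in: *For Grade 4 infusion-related reactions, permanent discontinuation is not conditional on this consultation.* Without this, the requirement to consult first would still apply to the item.

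The cost is two short edits in a protocol amendment or a clarification letter, a route that the amendment history shows this trial has already used. No data collection or analysis changes.
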